2.1 STUDY DESIGN

This study will be a retrospective chart review of structured and unstructured data from EHRs stored at Sinai Health. Pentavere's DARWENT™ technology will be trained to extract data variables from the structured and unstructured EHR data (Table 1). CCI

[REDACTED]. Once the data variables are extracted from the EHRs, descriptive analyses will be conducted.

E8 CDA
template.docx

Data extracted will include

Study population

The study period will extend from 01 January 2016 to 01 October 2021 (Figure 1). All female patients who are ≥18 years of age and are diagnosed with HR+/HER2- ABC/MBC and received a CDK4/6 inhibitor at Sinai Health during the study period will be included in the study. It is estimated that there will be approximately 300 diagnoses of MBC within the study period at Sinai Health, of which approximately 180 will be HR+/HER2-. Follow-up data from EHRs will be included up to the extent that they are available within the study period. Pre-index data (stage at initial breast cancer diagnosis, treatment being received at ABC/MBC diagnosis) may be extracted from EHRs up to 12 months before the index date.

PFIZER CONFIDENTIAL

[figure not shown]

Figure 1. Study Design Flow Chart

Data source

Patients will be selected with dates of diagnosis of HR+/HER2- ABC/MBC between 01 January 2016 and 01 July 2021. Study data will be extracted from Sinai Health EHRs up to 12 months before ABC/MBC diagnosis until the end of the study period (01 October 2021, Figure 1)

Treatment/cohort labels

1. Patients treated with Palbociclib combination treatment
2. Patients treated with CDK4/6 inhibitor.

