4.4 SUBGROUPS

Subgroup analyses for the primary and secondary objectives will be conducted in patients who are potentially pre-menopausal, where possible. Patients who are 50 years old or younger and are on a LHRH antagonist will be included in this subgroup. Subgroup analyses will be descriptive in nature and will depend on adequate sample size.

The secondary objective will include the following subgroups for specified analyses, where possible:

[figure not shown]
- Pre-CDK subgroup is defined as ABC/MBC patients starting systemic therapy before the introduction of CDK 4/6 inhibitor (January 2016 to May 2016).
- Post-CDK subgroup is defined as ABC/MBC patients starting systemic therapy after the introduction of CDK 4/6 inhibitor (January 2019 to May 2019).

CCI

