Describing pre- and post-CDK treatment patterns and sequencing in ABC/MBC patients is one of the secondary objectives of this study. To explore treatment patterns and sequencing before the introduction of CDK4/6 inhibitor (“pre-CDK” subgroup), ABC/MBC patients diagnosed and starting systemic therapy before the introduction of Palbociclib in Canada (i.e. January 2016 to May 2016) will be investigated. To explore treatment patterns and sequencing after introduction of CDK4/6 inhibitors, a similar length of time (i.e. January – May) will be investigated; however, this will be done in 2019 to allow for sufficient time for education and uptake of CDK4/6 inhibitor usage in

PFIZER CONFIDENTIAL

[figure not shown]
clinical practice (“post-CDK” subgroup). The above dates are the time periods we propose based on clinical relevance, but they are contingent upon clinician input and review of primary objective results and are subject to change.

Treatment patterns for systemic therapy for the pre-CDK subgroup and post-CDK subgroup will be described. Sequencing of therapies received after CDK treatment will be described. Continuous and categorical variables will be described using methods outlined in Section 7.1 of this document. Bar charts may also be used to illustrate changes in treatment patterns over time if appropriate. The above-mentioned analyses will use the following or similar R packages: ‘tables’ and ‘ggplot’.

Type	Supports Protocol Objective Number	Endpoint	Population	Statistical Method/Test	Covariates used	Method of adjustment for missing values	Role of the analysis related to study objectives
Table	2	Not applicable	-Pre-CDK subgroup -Post-CDK subgroup	Descriptive stats Comparisons tests (e.g. t-test, ANOVA, Wilcoxon, Fischer)	Systemic therapies	Missing data will be summarized in table. Missing days from dates will be handled as per section 6 of this document.	To describe treatment patterns pre and post CDK.
Bar chart	2	Not applicable	-Pre-CDK subgroup -Post-CDK subgroup	Descriptive stats	Systemic therapies	Missing data will be excluded. Missing days from dates will be handled as per section 6 of this document.	To illustrate treatment patterns over time.

Time to event analysis:

PFIZER CONFIDENTIAL

CCI

Numbers

at risk and cumulative incidence will be reported for each curve. **CCI**

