Age	N Mean (SD) Median Q1, Q3 Minimum-Maximum		
Sex	Female Male Unknown		
ECOG	0 1 2 3 4 Unknown		
Organ level metastatic site	Bone Brain Lungs Liver		
Number of metastatic sites	0 1 2 3 4		
Comorbidities	Atrial fibrillation Hypertension Coronary Artery Disease/Myocardial infarction/Angina Diabetes Mellitus Stroke		
Tumour stage at diagnosis	I II III IV Unknown		
Tumour grade	1		

PFIZER CONFIDENTIAL

2		
3		
Unknown		
Tumour histology		
Lobular Carcinoma		
Ductal carcinoma		
Mixed		
DCIS		
LCIS		
Other		
Unknown		
ER Receptor status		
Positive		
Negative		
Unknown		
PR Receptor status		
Positive		
Negative		
Unknown		

^a Defined as patients who were diagnosed between March 10, 2019 – March 10, 2020.

^b Defined as patients who were diagnosed between March 11, 2020-March 11, 2021.

Treatment patterns and changes:

Table 6: Line 1 Treatment Patterns in patients who received Palbociclib

Variables	Overall (N=) ^a	Pre-menopausal patients (N=) ^b
Chemotherapy N, Mean Tx duration (SD)		
Chemo drug 1, n (%)		
Chemo drug 2, n (%)		
...		
Targeted therapy N, Mean Tx duration (SD)		
Targeted drug 1, n (%)		
Targeted drug 2, n (%)		
...		
...(Any other Class of therapy observed)		

^a Includes all patients who received Palbociclib

^b Includes patients who received Palbociclib and who are potentially in pre-menopause. Please refer to section 4.4 of this document for further details about how this group is defined.

Treatment patterns and changes in patients who received Palbociclib:

[figure not shown]

Figure 1: Classes of treatments over time in patients who received Palbociclib. Similar plots will be created for all lines of therapy. Stacked bar charts can be either absolute values (as shown) or percentages, as required.

Figure 2: Sankey Diagram of treatment of patients who received Palbociclib

Treatment patterns and changes in patients who received Palbociclib who are potentially in pre-menopause.

[figure not shown]
Figure 3: Classes of treatments over time in patients who received Palbociclib who are potentially in pre-menopause. Please refer to Figure 1 for reference as to how bar charts will look. Similar plots will be created for all lines of therapy.

GER CONFIDENTIAL

Figure 4: Sankey Diagram of treatment of patients who received Palbociclib who are potentially in pre-menopause

PFIZER CONFIDENTIAL

Pre and Post-CDK treatment patterns:

Table 7: Pre and post-CDK treatment patterns and sequencing in patients

	Pre-CDK ^a			Post-CDK ^b		

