	Line 1	Line 2	Line 3	Line 1	Line 2	Line 3
Chemotherapy N, Mean Tx duration (SD)						
Chemo type 1, n (%)						
Chemo type 2, n (%)						
...						
Targeted therapy N, Mean Tx duration (SD)						
Targeted type 1, n (%)						
Targeted type 2, n (%)						
...						
...						

^a Defined as treatment started between January 2016-May 2016^b Defined as treatment started between January 2019- May 2019

Table 8: Sequencing of therapies after CDK 4/6 inhibitor

[figure not shown]
	Overall (N=)
Post-CDK received in L1	
Medicinal product name 1, n (%)	
Medicinal product name 2, n (%)	
...	
Post-CDK received in L2	
Medicinal product name 1, n (%)	
Medicinal product name 2, n (%)	
...	
Post-CDK received in L3	
Medicinal product name 1, n (%)	
Medicinal product name 2, n (%)	
...	

Bar charts

Figure 5: Classes of treatments over time in all patients. Please refer to Figure.1 for reference as to how bar charts will look. Similar plots will be created for all lines of therapy.

PFIZER CONFIDENTIAL

Time to event analyses in all patients:

Figure 6: TTNT1 in all patients by type of treatment

Figure 7: TTNT2 in all patients by type of treatment

Figure 8: TTC in all patients by type of treatment

Figure 9: Overall Survival in all patients by type of treatment

Table 9: Length of Line 1 treatment in short term vs long term responders

Variables	Short term responders (n=) ^a	Long term responders (n=) ^b
Chemotherapy N, Mean Tx duration (SD)		
Chemo type 1		
N		
Mean (SD)		
Median		
Q1,Q3		
Minimum-Maximum		
Chemo type 2		
N		
Mean (SD)		
Median		
Q1,Q3		
Minimum-Maximum		
...		
Targeted therapy N, Mean Tx duration (SD)		
Targeted type 1		
N		
Mean (SD)		
Median		
Q1,Q3		
Minimum-Maximum		
Targeted type 2		
N		
Mean (SD)		
Median		
Q1,Q3		
Minimum-Maximum		
...		

^a Defined as those who are on first line therapy for up to 3 to 6 months

^b Defined as those who are on first line therapy for more than 6 months

Time to event analyses in pre-menopausal patients:

Figure 10: TTNT1 in patients who are potentially in pre-menopause by type of treatment

Figure 11: TTNT2 in patients who are potentially in pre-menopause by type of treatment

Figure 12: TTC in patients who are potentially in pre-menopause by type of treatment

Figure 13: Overall Survival in patients who are potentially in pre-menopause by type of treatment

Table 10: Length of Line 1 treatment in short term vs long term responders in pre-menopausal patients^a

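### Table 7 sets Lines 1–3 of 2016 and 2019 starters side by side with at most 64–69 versus 28–33 months of observation, so later-line counts and mean durations are lower in the post-CDK group even if practice is identical

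*SAP*

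**What the plan says.** SAP 4.4 defines two subgroups for the secondary objective by when the patient started treatment: "starting systemic therapy before the introduction of CDK 4/6 inhibitor (January 2016 to May 2016") and "starting systemic therapy after the introduction of CDK 4/6 inhibitor (January 2019 to May 2019"). SAP 7.2 explains the second window: "a similar length of time (i.e. January – May) will be investigated; however, this will be done in 2019". The stated reason for 2019 is time for education and uptake. Follow-up is not mentioned.

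The end of observation is one calendar date for everyone. SAP 2.1 states: "The study period will extend from 01 January 2016 to 01 October 2021". It adds: "Follow-up data from EHRs will be included up to the extent that they are available within the study period". Extraction runs "until the end of the study period (01 October 2021, Figure 1").

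The output is "Table 7: Pre and post-CDK treatment patterns and sequencing in patients". Its shell has columns for Lines 1, 2 and 3 under each subgroup. Each class of therapy has a row of the type "Chemotherapy N, Mean Tx duration (SD"), with n (%) by drug beneath. The analysis table in SAP 7.2 also lists comparison tests for this output, although SAP 3.1 rules out formal hypotheses.

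The visible text gives no common follow-up, no rule for therapy still ongoing at the cut-off, and no denominator for Lines 2 and 3. SAP 7.2.2 assigns the pre/post analysis descriptive statistics and bar charts, with no strata. The Kaplan-Meier curves it lists are exploratory; they are stratified by systemic therapy or belong to the COVID-19 analysis, and none is by pre/post-CDK subgroup. Protocol 9.9 does not name unequal follow-up as a limitation.

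**The concern.** Whether a second or third line is recorded depends on how long the patient is watched. So does the recorded length of a line that is still running when the data stop. The two groups differ by 36 months in the time available for both, and Table 7 has no column or rule that takes this out.

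Three features of the post-CDK columns would follow from the cut-off alone:

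- fewer patients reaching Lines 2 and 3;
- shorter mean observed treatment durations;
- a Line 2 and Line 3 drug mix weighted toward patients whose earlier lines ended sooner.

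This is the main visible table for the secondary objective. A reader would naturally take such differences as the effect of introducing CDK4/6 inhibitors.

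**Working it through.** **1. Potential follow-up (exact).** Days from the first and last possible start to 01 October 2021, divided by 30.4375:

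| Start | Days | Months |
|---|---|---|
| 01 Jan 2016 | 2100 | 69.0 |
| 31 May 2016 | 1949 | 64.0 |
| 01 Jan 2019 | 1004 | 33.0 |
| 31 May 2019 | 854 | 28.06 |

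The entry windows are indeed of similar length (152 and 151 days). The gap in potential follow-up is 36 months. These are maxima: death and loss to follow-up shorten both.

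**2. Illustration with no true difference between groups.** The plan gives no line durations, so the following are assumptions:

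- Line lengths are exponential and the same in both groups. Median PFS figures from protocol section 7 stand in for them: 24.8 or 14.5 months for line 1 and 9.2 months for line 2.
- The next line starts when the previous one ends.
- Follow-up F is uniform over 64–69 or 28–33 months.
- Deaths are exponential with rate δ. Protocol section 7 gives 22% five-year survival for stage IV, so median survival = 60 × ln 2 / (−ln 0.22) = 27.5 months. Runs with no deaths and with an assumed 36 months are shown for range.

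With λ1 and λ2 = ln 2 / median:

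P(line 1 ended) = λ1/(λ1+δ) × [1 − exp(−(λ1+δ)F)]

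P(line 2 ended) = λ1λ2/(λ2−λ1) × {[1 − exp(−(λ1+δ)F)]/(λ1+δ) − [1 − exp(−(λ2+δ)F)]/(λ2+δ)}

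Worked at the mid-points, with line 1 median 24.8 (λ1 = 0.02795):

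- No deaths: 1 − exp(−0.02795 × 66.5) = 0.844, and 1 − exp(−0.02795 × 30.5) = 0.574.
- Median survival 27.5 months (δ = 0.0252): 0.526 × [1 − exp(−0.05315 × 66.5)] = 0.51, and 0.526 × [1 − exp(−0.05315 × 30.5)] = 0.42.

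Averaged over each follow-up range, pre-CDK v post-CDK:

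| Medians, line 1 / line 2 | Median survival | Line 1 ended | Line 2 ended |
|---|---|---|---|
| 24.8 / 9.2 | no deaths | 84% v 57% | 76% v 38% |
| 24.8 / 9.2 | 36 | 57% v 45% | 43% v 27% |
| 24.8 / 9.2 | 27.5 | 51% v 42% | 37% v 25% |
| 14.5 / 9.2 | no deaths | 96% v 77% | 90% v 54% |
| 14.5 / 9.2 | 36 | 71% v 62% | 55% v 39% |
| 14.5 / 9.2 | 27.5 | 65% v 58% | 48% v 36% |

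**3. Mean observed duration.** The plain mean of line 1 as recorded is [1 − exp(−(λ1+δ)F)]/(λ1+δ). For a 24.8-month median this is 30.2 v 20.5 months without deaths and 18.3 v 15.1 months with 27.5-month survival. A filter on line starts alone leaves these figures unchanged, because line 1 starts at time zero in both groups.

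**4. Common horizon.** The last possible 2019 starter has 28.06 months, so 28 is the longest whole-month horizon that every patient could complete. With F = 28 in both groups the model difference is zero. For 14.5 / 9.2 without deaths, line 1 has ended in 74% and line 2 in 49% of each group. For 24.8 months without deaths, mean observed line 1 is 19.4 months in each.

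**5. Subgroup size.** The amendment logs put the cohort below 30% of 180, so under 54. If accrual were even over the 66 months from 01 January 2016 to 01 July 2021 (assumption), a five-month window holds about 54 × 5/66 = 4 patients.

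**The case against.** The strongest case against has four parts.

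- **Deaths shrink the gap.** This stands. With survival based on the protocol's stage IV figure, the line 1 gap for 24.8 / 9.2 months falls from 27 to 9 points and the line 2 gap from 38 to 12. The no-death figures are an upper extreme, but the direction is the same in every scenario above.
- **The model is not the SAP population.** This also stands. The full analysis set requires CDK4/6 inhibitor treatment, and 2016 starters, who began before its introduction, can qualify only by receiving one later. That selection pushes later-line use up in the pre-CDK group whatever the follow-up. It works in the same direction and does not offset the follow-up effect, but the whole pre/post contrast cannot be put down to follow-up.
- **The subgroups will be tiny and the analysis is descriptive.** SAP 4.4 makes these subgroups conditional on feasibility, and outputs may change with sample size. With about four patients per window, imprecision may outweigh the bias. It does not remove it, and a descriptive contrast can still mislead.
- **The window dates may change.** SAP 7.2 allows this, but moving the dates does not equalise follow-up unless a horizon is set.

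A reader might infer more than the documents support. Table 7 cannot show lines 2 and 3 as starting earlier, because it has no time-to-line row. Drug percentages within a line need not be lower, because the shell fixes no denominator. Nor do post-CDK lines 2 and 3 come only from patients who ended earlier lines quickly: 28–33 months exceeds a 24.8-month median, and more than half would have ended line 1 in the no-death case.

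**Conclusion.** The point holds. Table 7 compares groups matched on entry-window length but with at most 64–69 versus 28–33 months of observation, and the visible text contains nothing that corrects for it. The follow-up figures are calendar arithmetic and rest on no model. They use the patient-level subgroup definition in SAP 4.4; the Table 7 footnote could be read line by line.

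The artificial difference under identical practice is 7 to 27 percentage points for line 1 ended and 12 to 38 points for line 2 ended. The range depends mainly on mortality and on the stand-in line durations. The sizes rest on exponential durations, PFS as a proxy for line length, and all-subtype stage IV survival, so they are illustrations and not predictions. Any observed difference would also contain real change in practice and the effect of the eligibility rule. This should be corrected before Table 7 is produced.

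**What to change.** In SAP 7.2 and the Table 7 footnotes:

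1. Cut observation in both groups at a common horizon from each patient's first qualifying systemic therapy start. Set it to the shortest potential follow-up in the post-CDK window: 28 months with the current dates, recalculated if the windows change.
2. Apply the cut to line starts and to treatment durations. Treat therapy ongoing at the cut as censored, and replace the plain mean with, for example, a Kaplan-Meier median or a restricted mean to 28 months.
3. For Lines 2 and 3, report two denominators: the number in the subgroup, and the number who ended the previous line within the horizon.
4. Show full follow-up of 2016 starters only as a supplementary column that is not set against 2019.
5. Add a footnote that the common horizon does not remove the selection from requiring CDK4/6 inhibitor treatment, which 2016 starters can meet only by receiving one later.

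The cost is SAP wording, a date filter and a censoring rule, with no new data. The downside is that lines begun and durations accrued after month 28 in the 2016 group leave the main comparison. The subgroups will probably remain very small.

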3 HYPOTHESES AND DECISION RULES

3.1 STATISTICAL HYPOTHESES

The planned data analyses are descriptive in nature and are subject to modification based on sample size and final data specifications. No formal hypotheses will be tested.

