4.3 OTHER ANALYSIS SET

The primary objective will include only patients who received at least one dose of Palbociclib during the study period.

The secondary and **CCI** objectives will include all patients in the full analysis set.

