7.2 STATISTICAL ANALYSES

Treatment patterns and changes:

Treatment patterns among patients with HR+/HER2- ABC/MBC receiving Palbociclib will be analysed as the primary objective of this study. This analysis will be conducted in all patients who have received Palbociclib combination treatment. Subgroup analyses on patients who are likely to be pre-menopause might also be conducted if applicable. This analysis will be descriptive in nature and is subject to modification based on sample size and final data specifications. No statistical tests will be utilized. Continuous and categorical variables will be described using methods outlined in Section 7.1 of this document. Sankey diagrams and/or bar charts may also be used to illustrate sequencing and changes in treatment patterns if appropriate. The above-mentioned analyses will use the following or similar R packages: 'tables', 'ggplot', and 'networkD3'.

Type	Objective	Endpoint	Population	Statistical Method/Test	Covariates used	Method of adjustment for missing values	Role of the analysis related to study objectives
Table	1	Not applicable	- All patients who have received Palbociclib	Descriptive stats	Systemic therapies	Missing data will be summarized in table.	To describe treatment patterns during

PFIZER CONFIDENTIAL

			combination treatment. - Pre-menopausal patients ^a			Missing days from dates will be handled as per section 6 of this document.	study period.
Bar chart	1	Not applicable	- All patients who have received Palbociclib combination treatment. - Pre-menopausal patients ^a	Descriptive stats	Systemic therapies	Missing data will be excluded. Missing days from dates will be handled as per section 6 of this document.	To illustrate changes in treatment patterns by year.
Sankey diagram	1	Not applicable	- All patients who have received Palbociclib combination treatment. - Pre-menopausal patients ^a	Descriptive stats	Systemic therapies	Missing data will be excluded. Missing days from dates will be handled as per section 6 of this document.	To illustrate sequencing of treatments.

^a Patients who are potentially pre-menopausal may be analyzed as a subgroup for this objective. Please refer to section 4.4 of this document for further details about how this group is defined.

Pre- and Post-CDK treatment patterns:

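### SAP 7.2 lets the pre- and post-CDK calendar windows change after the primary results are reviewed, which could bias the described pre/post change

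*SAP*

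**What the plan says.** SAP 4.4 gives the two subgroups as definitions. For the earlier one: "Pre-CDK subgroup is defined as ABC/MBC patients starting systemic therapy before the introduction of CDK 4/6 inhibitor (January 2016 to May 2016". For the later one: "Post-CDK subgroup is defined as ABC/MBC patients starting systemic therapy after the introduction of CDK 4/6 inhibitor (January 2019 to May 2019". The footnotes to SAP Tables 4 and 7 repeat the dates. None of these places makes the dates depend on any result.

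SAP 7.2, under the pre- and post-CDK heading, explains the choice. The post window has a similar length and the same months as the pre window, and it sits in 2019 to leave time for uptake. The section then calls the dates proposals and adds that "they are contingent upon clinician input and review of primary objective results and are subject to change".

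The primary analysis in SAP 7.2 covers systemic therapies in palbociclib-treated patients. It includes a bar chart whose stated role is "To illustrate changes in treatment patterns by year". The role of the secondary table is "To describe treatment patterns pre and post CDK", also on systemic therapies. Under SAP 4.3, the secondary and further "objectives will include all patients in the full analysis set", and that set contains the palbociclib-treated patients of the primary analysis.

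**The concern.** Clinician input given before results exist is unobjectionable. The difficulty is the second condition. Whoever reviews the primary results will have seen how therapy varies by year in overlapping patients before it is settled which months stand for the period after introduction. If the choice responds to what was seen, the reported change mixes any real change with the chance variation that made one window look more striking than another.

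Calling the analysis descriptive does not remove this, because a description can be biased without any test being run. At stake is the credibility of the pre/post description under the only secondary objective that is visible in the protocol and SAP.

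**Working it through.** **Is there a safeguard elsewhere?** The plan has no figure of its own to reproduce: protocol 9.5 says that sample size calculations do not apply. I therefore looked for text that would limit the change.

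- Protocol 9.7 promises an amendment for major changes to primary endpoint definitions or their analyses. The windows belong to a secondary objective.
- Protocol 9.8 locks the dataset before analysis. That fixes the data, not the windows.
- SAP 3.1 and SAP 8 allow modification for sample size and data specifications. They do not mention results, so SAP 7.2 goes further.
- I found no rule for changing the windows, no freeze date, and no duty to report the stated windows beside changed ones.

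**How far can the windows move?** Diagnoses run from 01 January 2016 to 01 July 2021 (protocol 9.2.1), which is 66 months. The pre window cannot start earlier and must precede palbociclib's introduction, so it is nearly fixed. If the January-to-May form is kept, the candidate post windows are those of 2017, 2018, 2019, 2020 and 2021. That is at most k = 5, and fewer once uptake time is required. I use k = 2 to 5.

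**Patients per window.** With uniform accrual (assumed), the expected count is N × 5/66.

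- N = 180 (protocol 9.5): 180 × 5/66 = 13.6, about 14.
- N = 54: 54 × 5/66 = 4.1, about 4. The reason columns of the amendment tables expect less than 30% of 180, and 0.30 × 180 = 54, so this is an upper bound.

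These counts go by diagnosis date, whereas SAP 4.4 defines the windows by start of systemic therapy. They are approximate.

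**Worst-case selection.** Suppose that the true share of patients on a given therapy is p in every window, so there is no real change. The pre window is fixed, and the post window with the highest share is picked from k. The pre share averages p, so the mean spurious difference is E[max] − p, where

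E[max] = (1/n) × Σ over x = 0 to n−1 of [1 − F(x)^k],

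and F is the Binomial(n, p) distribution function.

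Example with n = 4, p = 0.5, k = 2: F(0) to F(3) are 0.0625, 0.3125, 0.6875 and 0.9375. Their squares sum to 1.453, so E[max] = (4 − 1.453)/4 = 0.637 and the difference is 13.7 points.

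Mean spurious difference in percentage points, p = 0.5:

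| Patients per window | k = 1 (fixed) | k = 2 | k = 3 | k = 5 |
|---|---|---|---|---|
| 4 | 0 | 13.7 | 20.5 | 28.0 |
| 14 | 0 | 7.5 | 11.2 | 15.4 |

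The assumed share matters. The same formula for k = 2 to 5 gives 12 to 27 points (n = 4) and 7 to 14 (n = 14) at p = 0.3. At p = 0.9 it gives 7 to 10 and 4 to 8.

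**The case against.** The strongest reply is that the calculation assumes someone deliberately picks the most extreme window, and nothing in the SAP says so. Its stated grounds are clinical relevance and time for uptake. With fewer than 54 patients expected, widening a window because it holds too few patients would be a natural and legitimate reason to change it. This stands: the figures are a ceiling on what the wording allows, not a forecast. It does not justify the wording, because sparse windows can be handled by a rule that looks only at patient counts.

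A reader might also infer that a change would be invisible. The documents do not support that. The tables carry the dates in footnotes, so a changed window could be seen against the SAP. SAP Figure 5 plots treatment classes over time in all patients, against which an odd window could be checked. The narrower gap is that nothing requires both sets of windows to be reported.

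A reader might further infer that SAP 4.4 and 7.2 flatly contradict each other. That is too strong: 4.4 applies its subgroups where possible and subject to adequate sample size, and 7.2 can be read as adding detail. The two should still agree on whether the dates are fixed.

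Finally, a reader might infer an inflated type I error. SAP 3.1 says "No formal hypotheses will be tested", so there is no formal error rate to inflate. The secondary table in SAP 7.2 does still list "Comparisons tests (e.g. t-test, ANOVA, Wilcoxon, Fischer", among others, which is a separate inconsistency. If Fisher's exact test were run at an assumed 0.05 with no true change (shares of 0.3 or 0.5), simulation gives rejection rates of 0.4% to 0.8% with a fixed window and 1.6% to 3.5% with the best of five, at 4 per window. At 14 per window the rates are 1.7% to 2.3% and 6.5% to 8.7%. The main harm is to the description.

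**Conclusion.** The point holds as a permitted source of bias. SAP 7.2 makes the windows depend on results that show the same kind of variable in overlapping patients, and no other text limits, freezes or requires disclosure of a change. The described pre/post change could be biased, chiefly through the post window.

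In the worst case the mean spurious difference is about 14 to 28 points at 4 patients per window and about 7 to 15 at 14 per window, against 0 with fixed windows. This rests on uniform accrual over 66 months, a constant true share of 50%, an unchanged pre window, and choice of the most favourable of two to five January-to-May windows. Shares further from 50% give smaller figures. A reader might infer that the sponsor plans to choose windows this way, or that the reported change will be exaggerated; the documents support neither. The analysis is secondary and descriptive, which limits the consequence, but the correction is cheap and worth making.

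**What to change.** - In SAP 7.2, remove the dependence on reviewing the primary results. Clinician input can stay if it comes first.
- In a dated SAP version, before any primary results are seen, fix both windows or a widening rule that uses patient counts only.
- Make SAP 4.4, SAP 7.2 and the footnotes to Tables 4 and 7 say the same thing about whether the dates are final.
- Report any window adopted later as a labelled post-hoc analysis beside the pre-specified one.

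The cost is a few SAP sentences and less freedom to adapt the windows after seeing results. If primary results have already been seen, the SAP should say so and keep the stated windows as the reference analysis.
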